4.4. Method of Assigning Patients to Treatment Group and Patient ID Number

Eligible patients who sign consent will be identified with the same Patient Identification Number assigned to the patient during the OLE study. All patients completing the OLE study with a

response to treatment and consenting will be eligible to screen. Once eligibility is confirmed, they will be randomized 1:1 to blinded treatment with oral relugolix with E2/NETA, once daily or placebo for up to 52 weeks.

4.5. **Removal of Patients from Therapy**

Completion of the Week 104 visit with appropriate safety follow-up defines completion of the study. Patients may withdraw consent to participate in the study and discontinue treatment at any time for any reason. Investigators or the medical monitor may remove patients from therapy under this protocol for reasons of safety and/or lack of compliance as discussed below. Patients removed from therapy for any reason will undergo the assessments for the Early Termination visit (see the Week 104 visit on the Schedule of Activities; Table 1-1) and will have a follow-up visit to assess safety approximately 30 days after the end of study drug treatment (i.e., after the patient's last dose of study drugs).

The following safety and/or compliance events will result in the removal of patients from therapy either permanently or until the etiology of the problem has been identified and resolved:

- Any adverse event that is intolerable to the patient and that cannot be ameliorated by the use of adequate medical intervention, or that in the opinion of the investigator or medical monitor would lead to an undue risk to the patient if dosing continued;
- If it is discovered after enrollment that a patient failed to meet protocol entry criteria and continued participation poses an unacceptable risk to the patient's health;
- If the following liver test abnormalities develop, study drug should be discontinued immediately with appropriate clinical follow-up (including repeat laboratory tests, until a patient's laboratory profile has returned to normal/baseline status):
 - \circ ALT or AST > 8 x ULN; or
 - o ALT or AST > 5 x ULN and persists for more than 2 weeks; or
 - \circ ALT or AST > 3 x ULN in conjunction with elevated total bilirubin > 2 x ULN or international normalized ratio (INR) > 1.5; or
 - o ALT or AST > 3 x ULN with appearance of fatigue, nausea, vomiting, right upper quadrant pain or tenderness, fever, rash and/or eosinophilia (> 5%);
- If an iron deficiency anemia related to heavy menstrual bleeding develops with a hemoglobin < 8g/dL and is unresponsive to iron supplementation;
- QT interval by the Fridericia correction (QTcF) prolongation of more than 500 msec read by a cardiologist;
- Evidence of endometrial hyperplasia or endometrial carcinoma on endometrial biopsy;
- If the patient has a Z-score < -2.0 or has a \ge 7% decrease in bone mineral density from the Parent study Baseline at lumbar spine, total hip, or femoral neck based on the OLE study Week 52 DXA assessment of bone mineral density;
- If the patient, in the opinion of the investigator or the medical monitor, is grossly noncompliant with the protocol's requirements. This may include < 75% compliance with the study drug for at least 2 months; not returning any feminine products despite having menstrual bleeding for > 2 consecutive cycles; or missing multiple study visits;
- If the patient becomes pregnant at any time after providing a signed informed consent form, the patient must be withdrawn immediately (see Section 7.8 for information on pregnancy reporting).

Should a patient fail to attend the clinic for a required study visit within the protocol-defined window, the site should attempt to contact the patient and reschedule the missed visit as soon as possible. The site should also counsel the patient on the importance of maintaining the assigned visit schedule and determine whether the patient can and/or should continue in the study based on previous noncompliance. In cases where the patient does not return for the rescheduled visit or cannot be reached to reschedule the missed visit, the site should make every effort to regain contact with the patient. The site should make at least 3 documented attempts to contact the subject by telephone, or if necessary by certified letter so that they can appropriately be withdrawn from the study with a primary reason of "Lost to Follow-up."

4.6. Contraception/Pregnancy Avoidance

In this study, medications and devices containing hormones for contraception are excluded. Patients must agree to use nonhormonal contraception throughout the study unless any of the following apply:

- Has a sexual partner(s) who was vasectomized at least 6 months prior to the Week 52/Baseline visit;
- Had a bilateral tubal occlusion (including ligation and blockage methods such as EssureTM) at least 4 months prior to the Week 52/Baseline visit (patients with Essure must have prior confirmation of tubal occlusion by hysterosalpingogram) and there must be no evidence of post-Essure syndrome;
- Has a nonhormonal intrauterine device (e.g., Paragard®) placed in the uterus;
- Is not sexually active with men; periodic sexual relationship(s) with men requires the use of nonhormonal contraception as described below;
- Practices total abstinence from sexual intercourse, as her preferred lifestyle; periodic abstinence is not acceptable.

The only acceptable methods of contraception for whom none of the above methods apply are:

- Condom (male or female condom) with or without spermicide (cream, spray, foam, gel, suppository, or polymer film);
- Diaphragm with spermicide (condom may or may not be used);
- Cervical cap with spermicide (condom may or may not be used); or
- Vaginal sponge impregnated with spermicide used with a condom.

Patients will be provided with information on acceptable methods of contraception as part of the informed consent process and will confirm with signing of the consent form that they understand the requirements for avoidance of pregnancy during the course of the study. Patients may not donate ova during the course of the study and for 2 months following the last dose of study drug.

A patient may start hormonal contraception 4 weeks after her last study dose of study drug provided her menstrual cycle has returned.

Urine pregnancy tests will be performed at monthly intervals during the study (including prior to receiving the first dose of study drug), and patients will receive continued guidance with respect to the avoidance of pregnancy as part of the study procedures. Patients who become pregnant during the study will be withdrawn from the study and followed for pregnancy outcome (see Section 7.8).

5. TREATMENTS

5.1. Treatments Administered

Approximately 360 patients completing the OLE study and meeting the definition of responder and meeting all other eligibility criteria will be randomized 1:1 to blinded treatment with oral relugolix with E2/NETA (relugolix with add-back) or placebo for up to 52 weeks.

- Group A: 52 weeks of oral relugolix with E2/NETA, once daily;
- Group B: 52 weeks of placebo relugolix plus a capsule of placebo estradiol/norethindrone acetate.

The placebo relugolix tablet is manufactured to match the relugolix tablet in size, shape, and color. The placebo capsule is designed to match the over-encapsulated estradiol/norethindrone acetate active product in size, shape, color, and odor.

After randomization, if the alkaline hematin analysis confirms the return of heavy menstrual bleeding (defined as menstrual blood loss of ≥ 80 mL) the patient will be offered retreatment at their next visit with open-label relugolix with add-back for the remainder of the treatment period. Descriptions of all study drugs are provided in Table 5-1.

Table 5-1 Description of MVT-601-035 Study Drugs

Name of Investigational Product	Blinded and Open-Label Relugolix	Relugolix Placebo	Blinded Estradiol / Norethindrone Acetate	Estradiol / Norethindrone Acetate Placebo	Open-Label Estradiol / Norethindrone Acetate
Formulation Description	Round film- coated pink tablet	Round film- coated pink tablet	A Swedish orange, over-encapsulated round film-coated white tablet with back-fill material	A Swedish orange capsule with placebo back-fill material	Round, white, biconvex, film- coated tablet
Dosage Form	Tablet	Tablet	Capsule	Capsule	Tablet
Unit Dose Strength	40 mg	0 mg	Estradiol 1.0 mg / Norethindrone acetate 0.5 mg	0 mg	Estradiol 1.0 mg / Norethindrone acetate 0.5 mg
Route of Administration/ Duration	Oral once daily for up to 52 weeks	Oral once daily for up to 52 weeks	Oral once daily for up to 52 weeks	Oral once daily for up to 52 weeks	Oral once daily for up to 52 weeks

5.2. Identity of Investigational Product

Relugolix has the chemical name 1-(4-{1-[(2,6-difluorophenyl)methyl]-5-[(dimethylamino)methyl]-3-(6-methoxypyridazin-3-yl)-2,4-dioxo-1,2,3,4-tetrahydrothieno[2,3-d]pyrimidin-6-yl}phenyl)-3-methoxyurea.

Estradiol (1.0 mg)/norethindrone acetate (0.5 mg) is a fixed-dose combination product.

5.2.1. Product Characteristics

Relugolix has no chiral centers. The compound is slightly to partially soluble in acidic solutions but essentially insoluble at neutral pH (pH 7) and above. It is partially soluble in polar organic solvents. The compound is provided as an immediate-release pink tablet using common excipients.

The fixed-dose combination tablet of estradiol 1.0 mg/norethindrone acetate 0.5 mg is encapsulated in a gelatin capsule with sufficient common back-fill material.

5.3. Randomization and Stratification

Patients are randomized 1:1 ratio to blinded treatment with oral relugolix with E2/NETA (relugolix with add-back) or placebo. Stratification factors for randomization are as follows:

- Baseline MBL volume in the Parent study ($< 225 \text{ mL vs} \ge 225 \text{ mL}$)
- Geographic region (North America vs Europe vs Latin America vs Rest of World)
- Duration of exposure to relugolix (28 weeks vs 52 weeks).

5.4. Directions for Administration

The study drugs should be taken in the fasted state (water, tea, or coffee are allowed) in the morning, at least 1 hour before breakfast. If dosing is missed in the morning for any reason, the study treatment may be taken later in the day, under fasting conditions, at least 1 hour before or 2 hours after eating a meal. The study drugs should be taken as close as possible to the same time of morning each day.

5.5. Dose Reduction/Dose Administration

No toxicity-related dose reductions of study drug are permitted. Patients who experience a grade 3 or greater toxicity that cannot be ameliorated using adequate medical intervention should have their treatment interrupted until the toxicity improves to a grade 2 or lower severity. Patients may subsequently be restarted on study drug with the written approval of the sponsor (or designee).

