Adverse events that occur during the study should be evaluated by the investigator and graded according to Common Terminology Criteria for Adverse Events (CTCAE). Episodic adverse events, such as vomiting, or those that occur repeatedly over a period of consecutive days are "intermittent". All other events are "continuous". Additional information on detecting, documenting, and reporting adverse events and serious adverse events are provided below. No toxicity-related dose reductions of study drug are permitted; however, study drug can be held for a period of up to 2 weeks for evaluation and treatment of an adverse event. The study drug may be restarted if deemed safe for the patient by the investigator.

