7.5. Adverse Events of Clinical Interest Reporting

Adverse events of clinical interest in this study are defined as any increase in ALT or AST \geq 3 x ULN.

Any ALT or AST elevation of this degree or greater occurring during the open-label Treatment period or Safety Follow-up period should be reported to the sponsor using the Serious Adverse Event Form within 24 hours of the study site personnel's knowledge of the event (see Section 7.6), even if the event does not meet serious adverse event criteria. Additional instructions for evaluating patients with an increase in ALT or AST ≥ 3 x ULN may be found in Appendix 5.

7.5.1. Criteria for Temporary Withholding of Study Drug in Association with Liver Test Abnormalities

Hepatic enzymes will be monitored in accordance with FDA drug-induced liver injury guidelines [FDA, 2009].

If the following liver test abnormalities develop, study drug should be withheld immediately with appropriate clinical follow-up (including repeat laboratory tests, until a patient's laboratory profile has returned to normal/baseline status), and the event reported as a serious adverse event:

- ALT or AST $> 8 \times ULN$; or
- ALT or AST > 5 x ULN and persists for more than 2 weeks; or

- ALT or AST > 3 x ULN and total bilirubin > 2 x ULN or INR > 1.5; or
- ALT or AST > 3 x ULN with appearance of fatigue, nausea, vomiting, right upper quadrant pain or tenderness, fever, rash and/or eosinophilia (> 5%).

Rechallenge may be considered if an alternative cause for the abnormal liver tests (ALT, AST, total bilirubin) is discovered and the laboratory abnormalities resolve to normal or Week 52/Baseline values. The investigator and sponsor must discuss and agree with any decision to rechallenge.

Rechallenge should not occur when the etiology of the liver test abnormalities is considered possibly drug-induced.

7.5.2. Criteria for Permanent Discontinuation of Study Drug in Association with Liver Test Abnormalities

Study drug treatment should be discontinued permanently if all of the following 4 criteria are met (i.e., potential severe drug-induced liver injury/Hy's law case):

- 1. AST or ALT increases to ≥ 3 x ULN; AND
- 2. Total bilirubin increases to $> 2 \times ULN$ or INR > 1.5; AND
- 3. Alkaline phosphatase value does not reach 2 x ULN; AND
- 4. No alternative cause explains the combination of the above laboratory abnormalities; important alternative causes include, but are not limited to the following:

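### Protocol 5.5 and 7.1.1 contradict each other on how long study drug may be held and who approves restart after the same grade 3 or higher adverse event, and the related sections do not settle it

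*Protocol*

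**What the plan says.** All references are to the current protocol, Amendment 1.

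- **5.5 Dose Reduction/Dose Administration.** Patients with grade 3 or greater toxicity that adequate medical care cannot relieve "should have their treatment interrupted until the toxicity improves to a grade 2 or lower severity". No maximum is given. On restart: "Patients may subsequently be restarted on study drug with the written approval of the sponsor (or designee".
- **7.1.1 Adverse Event.** After repeating that toxicity-related dose reductions are not allowed, it states that "study drug can be held for a period of up to 2 weeks for evaluation and treatment of an adverse event". On restart: "The study drug may be restarted if deemed safe for the patient by the investigator". No grade is excluded and the sponsor is not mentioned.
- **4.5 Removal of Patients from Therapy.** The listed events lead to removal that is either permanent or lasts until the cause is found and resolved. The first is an adverse event that the patient cannot tolerate and medical care cannot relieve, or that would put her at undue risk. The section also says: "Patients removed from therapy for any reason will undergo the assessments for the Early Termination visit". A safety visit about 30 days after the last dose follows.
- **6.3 Early Termination Visit and Safety Follow-up Visit.** The Early Termination visit is for patients who withdraw from the study before Week 104.
- **Liver tests.** In 4.5: "If the following liver test abnormalities develop, study drug should be discontinued immediately". In 7.5.1, for the same four criteria: "If the following liver test abnormalities develop, study drug should be withheld immediately". Section 7.5.1 then allows rechallenge under conditions: "The investigator and sponsor must discuss and agree with any decision to rechallenge".
- **Appendix 5.** The withholding rule is written for blinded relugolix monotherapy, relugolix with add-back, or placebo.

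**The concern.** A site faced with a grade 3 event has no single instruction. If it follows 7.1.1, it may restart drug on the investigator's judgement without the written sponsor approval that 5.5 demands. If it follows 5.5, it may hold drug for longer than 7.1.1 allows. If it treats the event as a removal under 4.5, it carries out end-of-treatment assessments on a woman who may be about to resume.

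The direct stake is consistent safety handling across about 240 planned sites. There is also a reporting consequence. SAP 9.1.4 and 9.1.5 tabulate events leading to drug withdrawal and to dose interruption separately, according to the action recorded on the eCRF. SAP 5.2 counts a patient who met withdrawal criteria but was not withdrawn as an important protocol deviation. Under conflicting rules, two sites can record the same event differently and both be following the protocol.

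**Working it through.** The plan states no figure on this point, so the check is a comparison of the texts.

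| Question | 5.5 | 7.1.1 | 4.5 | 7.5.1 (liver only) |
|---|---|---|---|---|
| Trigger | Grade 3 or higher, not relieved by medical care | Any adverse event | Intolerable and not relieved, or undue risk; liver criteria; others | Four liver criteria |
| Maximum hold | None; until grade 2 or lower | 2 weeks | None; permanent, or until cause resolved | None; follow-up until normal or baseline |
| Who approves restart | Sponsor or designee, in writing | Investigator | Not stated | Investigator and sponsor together |
| Early Termination assessments | Silent | Silent | Yes, whatever the reason | Silent |

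**Step 1: do 5.5 and 7.1.1 cover the same event?** Yes. A grade 3 toxicity that cannot be relieved meets the 5.5 trigger. It is also an adverse event needing evaluation and treatment, so it falls under 7.1.1, which excludes no grade.

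**Step 2: do they give the same answer?** No. Take, for illustration, an event that needs 4 weeks to reach grade 2. Section 5.5 permits the whole hold. Under 7.1.1 the hold exceeds the limit by 28 − 14 = 14 days. The approver also differs: the sponsor in writing in one section, the investigator in the other.

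**Step 3: is there an order of precedence?** Neither section refers to the other, and nothing else in the protocol ranks them.

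**Step 4: does 4.5 resolve it?** No. Its first trigger overlaps the 5.5 trigger, since both turn on failure of adequate medical intervention. It allows temporary removal, but the Early Termination requirement has no exception for it, while 6.3 attaches the visit to leaving the study. A temporary removal therefore brings end-of-treatment assessments under 4.5 that 6.3 does not foresee.

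**Step 5: liver criteria.** The four thresholds are the same in 4.5 and 7.5.1, but the verbs differ (discontinue, withhold). The opening of the 4.5 list allows removal that ends when the problem resolves, so the two can be read together. The separate rule for permanent discontinuation in 7.5.2 is not part of the conflict.

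**Step 6: Appendix 5.** Protocol 5.1 has two randomized groups, relugolix with E2/NETA and placebo. Neither is relugolix monotherapy.

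**Step 7: does a hold take a woman out of the randomized period in the analysis?** SAP 4.3.1 sets the last randomized dose as the last one received, before retreatment or on the Week 104 visit date. SAP 4.3.4 computes duration as last dose − first dose + 1. For doses from Day 1 to Day 365 this is 365 − 1 + 1 = 365 days, however many days between were held. Censoring in SAP 7.3.1.2 follows feminine product collection, not daily dosing. A woman who is held and restarted stays in.

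**The case against.** The best defence is that 5.5 is the specific rule for severe, unrelieved toxicity, 7.1.1 the general rule, and 7.5.1 the liver rule. This is a sensible reading and may be what was meant. The protocol does not say so, however, and the reading does not explain why temporary removal in 4.5 brings Early Termination assessments.

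On that last part the defence is stronger. Section 4.5 asks for the assessments of the visit, and Table 1-1 labels the column as early termination of study drug. Sections 5.5 and 7.1.1 never call a hold a removal, and the 4.5 trigger is worded by tolerability, not by grade. A reader might infer that a long hold ends the woman's participation. The documents do not go that far: the hold sections are silent on the visit, so this is an unclear overlap, not a direct contradiction.

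The liver mismatch is softened by the opening of the 4.5 list, as shown above. The monotherapy phrase in Appendix 5 is a stray reference. The same sentence names relugolix with E2/NETA, which is also the content of open-label retreatment, and 7.5 refers to an open-label period.

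A reader might also infer a material bias in the primary endpoint: a woman sent to Early Termination is censored, while one who is held and restarted can relapse because of the hold. One could assume that 5% of 180 women in the relugolix group (9 women) are affected. At the planned 60% rate, switching all nine from censored to relapse gives 0.60 × 171/180 = 0.57 if early, or 0.60 × 99/108 = 0.55 if just before Week 76, a drop of 3 to 5 points against a planned difference of 20. The documents do not support this as an estimate. They give no hold rate. The figure needs every held woman to relapse and every one of them otherwise to be censored. Nothing in them says that a hold of a few weeks produces bleeding of 80 mL or more: Week 56 is an estradiol sampling time, no more. Any such bias would also run against relugolix.

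**Conclusion.** The contradiction between 5.5 and 7.1.1 on maximum hold and restart approver is explicit and should be corrected. The mismatch between 4.5 and 6.3 on Early Termination assessments is real but less direct. The liver wording and the Appendix 5 reference are minor and belong in the same correction.

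The consequence is for safety handling and consistent recording. Its size, and any effect on the Week 76 sustained responder rate, cannot be computed from the documents. The point does not put the primary analysis in doubt. It rests on the assumption that no document outside the protocol and SAP, such as the Study Reference Manual, sets an order of precedence; even if one did, the protocol text would still conflict.

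**What to change.** The sponsor should reconcile Protocol 4.5, 5.5, 6.3, 7.1.1, 7.5.1 and Appendix 5, most simply in one table to which each section refers. For each trigger, the table should give one hold rule, one restart approver and one statement of whether Early Termination assessments apply. It should cover blinded and open-label drug, and the monotherapy reference should go. Which hold length, approver or liver rule is right is a clinical decision for the sponsor; none is proposed here.

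The cost is a clarifying amendment, with the ethics committee submission that Protocol 10.2.1 requires, and notice to sites. No SAP text needs to change. A supportive analysis that censors women at the start of a hold would be a matter of preference. It could itself introduce informative censoring, and it would need interruption dates: SAP 9.1.5 shows only an action-taken field on the adverse event page, so their availability would have to be confirmed.

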5.6. Storage, Packaging, and Labeling

Study drug should be stored in an appropriate, limited-access, secure location within a temperature range of $20-25^{\circ}\text{C}$ ($68-77^{0}\text{F}$) (with excursions permitted \pm 5°C) to 15 - 30°C (59 - 86^{0}F) permitted until it is used or returned to the sponsor (or designee). Study drug should be stored protected from light. A daily temperature log of the drug storage area must be maintained every working day. Study drug must be stored under the conditions specified on the label, and remain in the original container until dispensed. Only patients enrolled in the study may receive study drug, and only authorized site staff may supply or administer study drug. Further guidance and information for final disposition of unused study drug are provided in the Study Reference Manual. The investigator is responsible for study drug accountability, reconciliation, and record maintenance, including receipt, reconciliation, and final disposition records and their secure storage.

Study drug will be labeled with the study protocol number, lot/batch number, expiry date, contents, directions for use, storage directions, clinical study statement, and any other labeling required by regulatory bodies in the study locations and will list Myovant Sciences GmbH as the sponsor. Patients will be instructed to store study drug at room temperature out of the reach of children.

All labels for relugolix and the estradiol/norethindrone acetate combination to be distributed will meet all applicable requirements of the US Food and Drug Administration (FDA) and Annex 13 of Good Manufacturing Practices: Manufacture of investigational medicinal products (July 2010) and/or other local regulations as applicable.

For randomized treatment, relugolix 40 mg will be supplied to the study site in blister cards. It will be co-packaged with the estradiol/norethindrone acetate. Open-label relugolix will be supplied in a bottle, and the open-label estradiol/norethindrone acetate will be supplied in a dial pack.

